### **3.2 Description of the Limbix Spark Program**

The Limbix Spark program is a 5 week program divided into levels intended to be completed weekly. A character called 'Limbot' is used as a guide. Limbot encourages the user in completing the behavioral activation program and provides personal examples of how he/she has undertaken behavioral activation therapy. Participants are instructed to complete a weekly Patient Health Questionnaire (PHQ)-8 assessment and participant symptom check in the mobile app. Tasks in the mobile app progress in a linear fashion-- i.e., each task must be completed to progress to the next task. Certain on-demand resources can be accessed in the app at any time, including emergency resources for patients experiencing thoughts of suicide or self-harm.

#### **3.2.1 Release Version 1 (Phase I)**

In Limbix Spark Version 1, the level system is framed around the idea that the app is teaching a skill (behavioral activation) and as participants progress through the program, they are building this skill and becoming more of an expert at it. The different levels are:

- Level 1 (Learning): Complete the learning part of the app
- Level 2 (Growing): Complete two activations

- Level 3 (Doing): Complete 3 activations
- Level 4 (Practicing): Complete 4 activations
- Level 5 (Mastering): Complete 5 activations

## UI Architecture

- **Tabs**
  - **Home tab.** The default screen the participant lands on when opening the app.
    - Shows participant current level and progress through it.
    - Shows participant the next action they need to take and provides direct access to that action (e.g. direct link to the next learning task or to review an activity).
    - Has crisis resources
    - Gives users the opportunity to provide product feedback.
  - **Learning tab.** Contains the 6 learning activities that are done during the program
    - Spark Overview
    - Mood & behavior 1 & 2
    - Breaking the cycle
    - Identify your values
    - Intro to activity scheduling
  - **Activities tab.**
    - View upcoming activities
      - See and edit scheduled activities
      - See and access activities that need review
    - View past activities
- **Activity scheduling button**
  - A floating button that is available on any screen and allows the participant to schedule a new activity

## Program Flow

- Level 1: Learning tasks
  - Onboarding.
    - Choose a Limbot
    - Enter name
    - View a walkthrough tutorial of the app interface.
    - Learn about weekly levels
      - Level 1 (Learning): Learning part of the app
      - Level 2 (Growing): Complete two activations
      - Level 3 (Doing): Complete 3 activations
      - Level 4 (Practicing): Complete 4 activations
      - Level 5 (Mastering): Complete 5 activations
  - Overview
    - Description of the program and how it works.
  - Mood and behavior 1 & 2
    - Learn the BA model of depression, focusing on the relationship between mood and behavior, and how that leads to a downward cycle of depression. The participant identifies common feelings and associated avoidance behaviors.
  - Breaking the cycle

- Learn how to break the downward spiral of depression by changing behavior
  - Identify values
    - Complete values clarification task and learn that choosing activities that align with values helps activities to be more effective in treating depression.
  - Intro to activity scheduling.
    - Participant is taught how to schedule activities using the activity scheduling button and tab.
    - View walkthrough tutorial of the Activities tab
    - See messaging that Level 1 is completed, Limbot acknowledgement and celebration!
    - Review next level's goals, and see a reminder about trying to advance one level per week
- Level 2 through 5: Activity scheduling
  - Schedule activities and review them
    - Participant schedules activity based on values.
    - Participant reflects on activity.
  - With each level they complete, they receive Limbot acknowledgement and a celebration. They then learn about their next goal.
    - If they complete level 5 before the 5 week study is done, participant is encouraged to continue scheduling activities in the app until the study ends.

### 3.2.2 Release Version 2 (Phase II)

Release version 2 expands on version 1 with the addition of new features and content based on product feedback from participants in a recently completed feasibility study of a Spark prototype. Minor modifications may also be made based on feedback from participants who received version 1.

Features/content to be added:

- Interactive psychoeducation focusing on the TRAP (trigger/response/avoidance pattern) and TRAC (trigger/response/alternative coping) model of depression and how it relates to behavior activation.
- A mood tracking feature that enables users to practice recognizing the relationship between their mood and their behavior. The feature will accomplish this by prompting users to log activities that they have done and how those activities made them feel. Users will also learn the concept of 'up activities' (those that improve their mood) and 'down activities' (those that worsen their mood) and will apply this concept by categorizing their logged activities as either 'up' or 'down'.
- The activity scheduling feature from version 1 will be enhanced by enabling users to 'favorite' their 'up' activities, and subsequently schedule favorited activities as behavioral activations. For example, if a user categorized 'riding my bike' an up activity, then that activity can be favorited and easily scheduled as a behavioral activation.
- Two new tabs in the user interface. A highlights tab that enables users to view summaries of their mood logs, up activities, favorites, and completed activities and associated values. A 'My Logs' tab has also been added that enables users to browse their mood-activity logs and behavioral activations by date.
- 

### 3.2.3 Release Version 3 (Phase II)

Release version 3 will further expand on version 2 with additional features and content based on product feedback from participants in a recently completed feasibility study of a Spark prototype. Minor modifications may also be made based on feedback from participants who received version 1 or version 2.

Features/content to be added:

- Animations and visual aids to further reinforce psychoeducational content and improve engagement.
- Problem-solving educational content, including how to apply the COPE (Clarity, Options, Perform, Evaluate) problem-solving framework. After learning the framework, users will be guided through an interactive process of applying this framework to overcome obstacles they may encounter when they complete scheduled activities.
- Mindfulness educational content and exercises, including application of mindfulness to mood-activity tracking and scheduled activities to enable users to better notice the relationship between mood and behaviors.
- Relapse prevention education and exercises, including development of a personalized relapse prevention plan. Users will be taught about the possibility of relapse, including potential triggers and early warning signs, and will then identify actions they can take if relapse occurs, including the application of skills that they learned throughout the rest of the program.

### **3.3 Description of the educational control**

#### **3.3.1 Description of educational control for Phase I**

The control mobile application will consist of 5 weeks of psychoeducational content with no active CBT or BA components. Consistent with FDA recommendations, the educational control will be similar to the Limbix Spark program in program duration (5 weeks), amount of content, modality of information delivery (mobile app) and design interface. The educational control will largely be based on the content of the NIMH Teenage Depression e-book (<https://www.nimh.nih.gov/health/publications/teen-depression/index.shtml>). This content will be supplemented with additional content from publicly available government-sponsored websites. Participants will be instructed to complete a weekly Patient Health Questionnaire (PHQ)-8 assessment and participant symptom check in the mobile app.

Program Flow:

- Lesson 1: What is Depression?
  - Description of what depression is, why you can't just "snap out" of it, and what causes depression
  - Additional reading links are provided
- Lesson 2: What are the signs and symptoms of depression?
  - Describes signs and symptoms of depression and addresses the fact that depression may affect different people in different ways
  - Additional reading links provided
- Lesson 3: How do doctors treat depression?
  - Describes psychotherapy and antidepressants
  - Additional reading links provided
- Lesson 4: What else can I do to stay healthy?
  - Describes other activities/healthy habits teens can try to stay healthy as they give treatment time to work
  - Additional readings links provided
- Lesson 5: How do I get help?

- Related resources and links provided
- 

### **3.3.2 Description of educational control for Phase II**

The control mobile application will consist of 5 weeks of psychoeducational content with no active CBT or BA components. Consistent with FDA recommendations, the educational control will be similar to the Limbix Spark program in program duration (5 weeks), amount of content, modality of information delivery (mobile app) and design interface. The educational control will consist of age-appropriate educational material on the neurobiology of depression. Market research in teens indicated equivalent expectations of treatment benefit for this program when compared to Limbix Spark. Participants will be instructed to complete a weekly Patient Health Questionnaire (PHQ)-8 assessment and participant symptom check in the mobile app.

#### **Program Flow:**

- Lesson 1: Understanding behavior
  - Introduction to program
  - The brain and behavior
  - Studying the brain
  - The teenage brain
- Lesson 2: Exploring the brain
  - Depression in the brain
  - Brain structure
  - Brain function
  - Depression in teens
- Lesson 3: Mastering Messengers
  - Messages in the brains
  - Neurotransmitters
  - Messengers in depression
  - Teens and transmitters
- Lesson 4: Riding the Wave
  - Hormones and behavior
  - Hormones in depression
  - Puberty & the brain
  - Puberty & depression
- Lesson 5: People & personality
  - What are genes?
  - Personality
  - Big 5
  - Big 5 interactive task
  - Genes & depression

### **3.4 Assessments**

Baseline and post-intervention assessments for participants and parents (if under 18) will be completed via a secure web portal. Weekly participant assessments will be completed in the mobile app. Weekly parent assessments will be completed via secure web portal.

## Schedule of Assessments:

|  | Baseline | Weekly during study | Post-intervention |
|--|----------|---------------------|-------------------|
| Patient Health Questionnaire (PHQ-8)                   | X        | X                   | X                 |
| Baseline Questionnaire- Participant                    | X        |                     |                   |
| Baseline Questionnaire- Parent                         | X        |                     |                   |
| Brief Resilience Scale                                 | X        |                     |                   |
| Generalized Anxiety Disorder (GAD-7)                   | X        |                     | X                 |
| PROMIS Pediatric Global Health Scale                   | X        |                     | X                 |
| PROMIS Parent Proxy Global Health Scale                | X        |                     | X                 |
| Mood and Feelings Questionnaire (Short Parent Version) | X        |                     | X                 |
| Participant Symptom Check- Participant                 |          | X                   |                   |
| Participant Symptom Check- Parent                      |          | X                   |                   |
| Post Program Questionnaire- Participant                |          |                     | X                 |
| Post Program Questionnaire- Parent                     |          |                     | X                 |
| System Usability Scale                                 |          |                     | X                 |
| User Engagement Scale                                  |          |                     | X                 |

## Description of Assessments

- The **Patient Health Questionnaire (PHQ-8)** is an 8-item self-report measure for screening for depression and for establishing depression severity. The PHQ-8 has been demonstrated to have high sensitivity and specificity in both adolescents and young adults. Clinically significant improvement is defined as a reduction in assessment score  $\geq 5$ . Post-intervention scores  $< 10$  are defined as remission.
- **Baseline Questionnaire- Participant and Parent:** Contains demographic, clinical history questions, and questions related to the impact of COVID-19.
- The **Brief Resilience Scale** is a 6 item self-report measure for assessing the ability to “bounce back” or recover from stress. It has been shown to be reliable and to measure a unitary construct.
- **7 item Generalized Anxiety Disorder scale (GAD-7).** The GAD-7 is a brief 7-item assessment for generalized anxiety disorder with satisfactory sensitivity and specificity. We will evaluate changes in anxiety symptoms given the high comorbidity between anxiety and depression.

- **PROMIS Pediatric Global Health Scale and PROMIS Parent Proxy Global Health Scale:** The PROMIS Pediatric and Parent Proxy Global 7+2 are 9-item measures that produce essentially a unidimensional measure of global health perception/well-being.
- **Mood and Feelings Questionnaire Short Parent version (MFQ-PS).** The MFQ-PS consists of a series of 13 descriptive phrases regarding how the subject has been feeling or acting recently and is a screening tool for depression in children and young people.
- **Participant Symptom Check- Participant & Parent.** Assesses parent and participant reported clinical concerns, severity level, and relationship of the clinical concern to the intervention.
- **Post-Program Questionnaire- Participant and Parent.** Contains questions about changes in treatment and questions about COVID19
- **System Usability Scale (SUS).** Provides a “quick and dirty”, reliable tool for measuring the usability of systems. It consists of a 10 item questionnaire with five response options for respondents; from Strongly agree to Strongly disagree. The SUS has become an industry standard, with references in over 1300 articles and publications. It is a very easy scale to administer to participants, can be used on small sample sizes with reliable results, and is valid – it can effectively differentiate between usable and unusable systems.
- **User Engagement Scale- Short Form (UES-SF).** A statistically reliable measure of self-reported user engagement. The form has 12 items and uses a 5 point Likert scale.

#### 4. Data Analysis and Data Monitoring

##### 4.1 Primary Outcome

###### Phase I

- Primary outcome measures will include feasibility data including: % of potential participants eligible to participate, % of eligible participants willing to participate, adherence to program (% of enrolled participants completing all sessions by post-treatment), participant satisfaction with the program, and clinical concern rates.

###### Phase II

- Between-subjects treatment-related change in depressive symptoms from baseline to 5-weeks as measured by PHQ-8 for those with baseline PHQ-8  $\geq 10$ .

##### 4.2 Secondary Outcomes/Analyses

###### Phase I

- Between-subjects treatment-related change in depressive symptoms as measured by PHQ-8 for those with baseline PHQ-8  $\geq 5$
- Remission rates based on PHQ-8  $< 10$  (sub-analysis for those with baseline PHQ-8  $\geq 10$ )
- Between-subjects treatment-related change in participant-rated anxiety symptoms and global functioning as measured by GAD-7 and PROMIS Pediatric Global Health Scale
- Between-subjects treatment-related change in parent-reported depressive symptoms and global functioning as measured by MFQ, and PROMIS Parent Proxy Global Health Scale
- Average treatment-related usability (SUS) and engagement (UES-SF) ratings
- Treatment-related program adherence and engagement based on mobile app analytics

###### Phase II

- Remission rates based on PHQ-8 < 10
- Between-group treatment-related differences in participant-rated anxiety symptoms and global functioning as measured by GAD-7 and PROMIS Pediatric Global Health Scale
- Between-group treatment-related differences in parent-reported depressive symptoms and global functioning as measured by MFQ, and PROMIS Parent Proxy Global Health Scale
- Average treatment-related usability (SUS) and engagement (UES-SF) ratings
- Between-group treatment-related differences in clinical concern rates and serious clinical concerns
- Between-group treatment-related differences in program adherence and engagement based on behavioral and mobile app analytics
- 

### 4.3 Tertiary/Exploratory Analyses

#### Phase I

- Exploratory analysis of moderating effects of demographic, clinical, COVID19-specific, and engagement factors on the relationship between treatment status and change in PHQ-8.

#### Phase II

- Exploratory analysis of moderating effects of demographic, clinical, COVID19-specific, resilience (BRS), and engagement factors on the relationship between treatment status and change in PHQ-8.
- Within-group (control group only) treatment-related change in depressive symptoms measured by the PHQ-8.
- Within-group (control group only) treatment related change in participant-rated anxiety symptoms and global functioning as measured by GAD-7 and PROMIS Pediatric Global Health Scale.
- Within-group (control group only) treatment related change in parent-reported depressive symptoms and global functioning as measured by MFQ, and PROMIS Parent Proxy Global Health Scale.
- Within-group (control group only) treatment-related differences in usability (SUS) and engagement (UES-SF) ratings.
- Within-group (control group only) treatment-related differences in clinical concern rates and serious clinical concerns.
- Within-group (control group only) treatment-related differences in program adherence and engagement based on behavioral and mobile app analytics.
- Between-group differences between Spark versions on clinical outcomes (PHQ-8, GAD-7, PROMIS, MFQ), program adherence, usability (SUS) and engagement (UES-SF).
- Factor analysis to investigate whether clusters of symptoms as indicated by PHQ-8 items are differentially impacted by Spark

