The research coordinator will direct participants and parents to a 21 CFR Part 11 compliant web portal where they will log in with their account credentials and complete baseline self-report assessments (see Assessments below). The research coordinator will send an email to the participant and their legal guardian (if required) with a safety plan document and instructions for completing and using this safety plan document should it be necessary. A reminder email to complete the safety plan will be sent to participants and their legal guardian (if required) 3 days later. The study coordinator will remain on the video call as participants and their legal guardian (if required) complete self-report assessments. After the study coordinator confirms that the assessments have been completed, the study coordinator will text or email the participant a link to download the study mobile app from the app store and will instruct them on how to download the Limbix mobile app. Participants will sign in using their login credentials, will undergo onboarding and be prompted to complete a baseline PHQ-8 in the mobile app. Completion of this initial PHQ-8 will be required for study participation to allow safety monitoring of symptom deterioration. Based on the randomization procedure, participants will have access to either the Limbix Spark intervention or the educational active control condition. The study coordinator will provide instructions on using the program to which the participant was assigned, answer any questions and end the video call.

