Both mobile programs (Limbix Spark and educational control) will be fully self-guided, completed by participants at home. Each program is designed to be completed over 5 weeks but users may progress through the program at their own pace. The Limbix Spark program progresses linearly, i.e., a task must be completed before a participant can progress to the next task. Content for a given week is not expected to take more than 60 minutes to complete. All participants will be prompted to complete a weekly PHQ-8 and clinical concerns questionnaire in the mobile app. Automated app notification reminders to complete these questionnaires will be sent. If users have not opened the app in 3 days, an automated app notification encouraging participants to use the app will be sent. An automated reminder notification will be sent 7 days before the end of the intervention period to remind participants that the intervention period will be ending in 7 days.

The legal guardian of participants under 18 will be emailed links to complete a parent-reported participant symptom check weekly. If they have not completed the questionnaire, they will be sent a reminder email 6 days later to remind them that the questionnaire is due the next day.

After the 5 week intervention period, participants and their legal guardian (if required) will be emailed links to complete post-intervention self-report assessments via secure web portal. Participants and their legal guardian (if required) will receive automated email reminders to complete the post-intervention assessments after 6 days if they have not completed the assessments. If participants or their legal guardian do not complete the post-intervention assessments within a week the research coordinator may reach out to participants or legal guardians via phone or email to encourage them to complete these assessments.

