In Phase II, for participants randomized to the treatment arm, if the participant does not complete the post-intervention assessments within 2 weeks from the end of the intervention period they will be considered lost to follow up. If a participant chooses to withdraw from the study at any point or the participant is deemed lost to follow up or is dropped from the study during the intervention period (5 weeks), access to the web portal and mobile app will be restricted at that time, otherwise access to the mobile app will be restricted at the end of the intervention period and access to the web portal will be restricted after post-intervention assessments have been completed or the participant is deemed lost to follow up (2 weeks after intervention period).

Participants randomized to the control arm will have two weeks to complete the post-intervention assessments. Once the post-intervention assessments have been completed or 2 weeks have passed, whichever occurs first, participants in the control arm will be granted access to the treatment condition (Limbix Spark) for 5 weeks. After access to Limbix Spark for 5 weeks, participants will have two weeks to complete another set of post-intervention assessments. If a participant chooses to withdraw from the study or the participant is deemed lost to follow up during the control app intervention period or Limbix Spark app intervention period (5 weeks

each), access to the web portal and mobile app will be restricted at that time. Otherwise, access to the mobile app will be restricted at the end of each intervention period and access to the web portal will be restricted after the second set of post-intervention assessments have been completed or the participant is deemed lost to follow up (2 weeks after Limbix Spark intervention period).

In Phase II, if participants report a change in their treatment for a mental health disorder while enrolled in the study, they may be withdrawn from the study.

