In Phase II, all participants will be compensated \$25 in the form of an electronic gift card for completing the baseline assessments and \$25 for completing each set of post-intervention assessments regardless of adherence to intervention (1 set of post-intervention assessments will be completed if assigned to the treatment arm and 2 sets of post-intervention assessments will be completed if assigned to the control arm-- 1 after completing the control app and another after subsequently completing the Limbix Spark app.) Gift cards will be emailed to participants.

If participants indicated during the consent process that they would be interested in participating in a post-intervention feedback interview, a research coordinator may contact participants and their legal guardian (if under 18) to set up this interview to be conducted over video conferencing. Participants who were randomized to the control condition may be contacted to complete these interviews following completion of the control arm, prior to starting the treatment condition. Participants and their legal guardian will be asked, separately, to answer questions about their experience with the program and provide feedback that may help improve the product for future users. These interviews may be audio-recorded with permission. These interviews are expected to take 1 hour, and participants and parent/legal guardians who participate will be compensated \$25/hr. Reimbursement will be prorated for interviews lasting less than 1 hour. For participants randomized to the control arm in Phase II, this interview will occur after completion of the Limbix Spark intervention period.

All relevant FDA requirements for the conduct of clinical trials will be followed, including registration on [clinicaltrials.gov](http://clinicaltrials.gov).

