Lastly, we will assess treatment adherence by evaluating treatment-related differences in rates of program completion and daily mobile app usage using independent samples (between treatment and control groups) or paired (within the educational control group) t-tests. We will also assess treatment-related differences in self-reported usability and engagement using the SUS and UES scales descriptively by comparing means and variability between groups and within group (control group only)

Statistical analyses for the primary outcome variable and between group differences in rates of clinical concerns rates will be conducted when N=60 (~30/grp) and N=120 (~60/grp) participants have completed Phase II. If no statistical differences are detected in the primary outcome variable, possible moderators of treatment status on the primary outcome may be evaluated, including age, concurrent treatment, and PHQ-8 score at baseline. Results of the interim analyses may be used to adjust recruitment targets for the remainder of the trial.

An effect size will be calculated for the primary outcome and may be used to determine sample size for a Phase III trial.

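### Phase II: the control group's symptom change on Spark has no comparator and no secured starting score, so it should not be called treatment-related

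*Combined protocol and SAP*

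**What the plan says.** Section 4.3 (Phase II) lists "Within-group (control group only) treatment-related change in depressive symptoms measured by the PHQ-8" as an exploratory item. Similar control-only items follow for GAD-7 and PROMIS, and for the parent-reported MFQ and PROMIS. No start point, end point, estimator or comparator is given for any of them.

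Section 3.1 sets the sequence. Controls have 5 weeks on the education app, and then: "Once the post-intervention assessments have been completed or 2 weeks have passed, whichever occurs first, participants in the control arm will be granted access". The second assessment follows: "After access to Limbix Spark for 5 weeks, participants will have two weeks to complete another set of post-intervention assessments". Between the two periods the app is closed: "access to the mobile app will be restricted at the end of each intervention period". On the number of assessments, the plan says "1 set of post-intervention assessments will be completed if assigned to the treatment arm and 2 sets of post-intervention assessments" for controls.

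On PHQ-8 collection, section 3.1 makes one in-app score mandatory, at first onboarding: "Completion of this initial PHQ-8 will be required for study participation to allow safety monitoring of symptom deterioration". After that, "All participants will be prompted to complete a weekly PHQ-8 and clinical concerns questionnaire in the mobile app". The schedule of assessments in section 3.4 has columns for baseline, weekly and post-intervention, and none for the switch to Spark.

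Section 4.4 (Phase II) applies a two-sided 0.05 level to all analyses. Its mixed model takes randomised arm as the main predictor. It names "independent samples (between treatment and control groups) or paired (within the educational control group) t-tests" for program completion and app usage.

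**The concern.** Two linked gaps affect the symptom scales.

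First, there is no concurrent comparator. The order is always education then Spark, and the Spark arm has already finished its only post-intervention set. Any fall in PHQ-8, GAD-7 or MFQ while controls use Spark mixes a possible Spark effect with elapsed time, order, carry-over and natural recovery. The planned model cannot separate these, because randomised arm is constant within the control group. Section 4.2 uses the same label, treatment-related, for the randomised between-group differences, so a reader could take the control-group result as a second demonstration of efficacy.

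Second, the starting score is not secured. In the Spark arm, missing the 2-week window means loss to follow-up. In the control arm, missing it still leads to Spark access. Those controls start Spark with no post-control PHQ-8, GAD-7, PROMIS or MFQ. Their last full set of scores is the enrolment baseline, taken before the whole education period. If that baseline, or an old weekly PHQ-8, serves as the start value, change that occurred on the education app is counted as change on Spark.

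**Working it through.** **The plan's own figure.** Section 2.1 gives N = 175 for d = 0.5, 80% power, two-sided 0.05 and 27% attrition. A two-sample t-test needs 64 per arm (power 0.801), so 128 in total, and 128 / 0.73 = 175.3. The figure reproduces, but it covers only the randomised comparison. The within-control analysis has no stated power or error-rate basis.

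**Timing.** A control who completes the post-control set gets Spark on completion, so that score sits at Spark start. A control who does not complete it starts Spark 5 + 2 = 7 weeks after enrolment. The app is closed during the 2-week gap, so weekly in-app scores cannot fill it.

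**Illustration 1: background change read as a Spark effect.** The documents give no SD of change and no natural-course rate, so both are assumed.
- Controls with paired data: n = 60 × 0.73 ≈ 44, from the Phase II minimum of 120 split equally and the plan's 27% attrition.
- SD of PHQ-8 change: 4, 5 or 6 points (assumed).
- True Spark effect: zero (assumed).
- Background fall over the Spark period: 0.5 to 2 points (assumed).
- Test: two-sided paired t-test on pre-post change. The plan does not specify this for PHQ-8.

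The noncentrality is √n × fall / SD on n − 1 = 43 degrees of freedom. For a 1-point fall and SD 5 it is 6.633 × 0.2 = 1.33, which gives p<0.05 with probability 0.254. The full grid for n = 44 is:

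| Background fall (points) | SD 4 | SD 5 | SD 6 |
|---|---|---|---|
| 0 | 5% | 5% | 5% |
| 0.5 | 13% | 10% | 8% |
| 1.0 | 37% | 25% | 19% |
| 1.5 | 68% | 49% | 37% |
| 2.0 | 90% | 74% | 58% |

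With all 60 controls and SD 5, the four non-zero rows become 12%, 33%, 63% and 86%.

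**Illustration 2: the missing start value.** Assume a steady fall of 0.2 points per week, a zero Spark effect, and 27% of controls without a score at the switch (the attrition figure, borrowed). The end point is 5 weeks after Spark start.
- All controls have a score at the switch: 5 × 0.2 = 1.00 point.
- The 27% use their week-4 education score (1 + 2 + 5 = 8 weeks): 0.73 × 1.0 + 0.27 × 1.6 = 1.16 points.
- The 27% use the enrolment baseline (5 + 2 + 5 = 12 weeks): 0.73 × 1.0 + 0.27 × 2.4 = 1.38 points.

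Over 0.1 to 0.4 points per week the three figures run 0.5 to 2.0, 0.58 to 2.32, and 0.69 to 2.76. The missing start value therefore adds to the problem, but the larger part is the lack of a comparator.

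**The case against.** The strongest reply is that these items are explicitly exploratory. The primary outcome is a randomised between-group comparison, and nowhere does the plan say that the control group's Spark-period change will be used as evidence of efficacy. That stands, and it limits the importance of the point. It does not remove it, because the label and the 0.05 level still apply to these items.

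Several stronger readings are tempting, and the documents do not support them:
- *A false benefit is very likely.* The illustration does not show this. At SD 5 the chance is 25% for a 1-point fall and 49% for 1.5 points, and drift and SD are both assumed.
- *The plan tests PHQ-8 change with a paired t-test.* It names that test for completion and usage. PHQ-8 is assigned to mixed models. A contrast of slopes between the two periods is also possible; it would still confound Spark with order, but the bias could then go either way.
- *Education-period change leaks into every control's estimate.* It can do so only for those who miss the post-control set, and the plan uses reminders, staff contact and payment to keep that group small.
- *Regression from the entry score of 10 or more drives the result.* Selection happened at enrolment and is not repeated at the switch, so much of this should be over by week 5. It matters mainly if the enrolment baseline is used as the start.
- *There is no current reference for a participant who worsens on Spark.* Weekly PHQ-8 is prompted in both programs and monitored, and the internal safety protocol mentioned in section 4.5.1 is not in the documents. No safety claim follows.
- *The usability, clinical-concern and adherence items share the defect.* There the wording can simply mean a difference between the two apps, natural symptom recovery does not bias them in the same way, and section 4.4 already treats usability and engagement ratings descriptively.

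**Conclusion.** The concern holds for the control-only symptom items: PHQ-8, GAD-7, PROMIS and MFQ. That the order is fixed, that nothing runs concurrently after the switch, and that no score is required at Spark start all follow from the text and need no assumption. These changes cannot support an effect of Spark.

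The size cannot be derived from the documents. Under the stated assumptions, a pre-post test with no Spark effect would be significant in about 8% to 90% of trials, against 5%. The width of that range shows how far the result would depend on an unknown natural course.

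The randomised primary comparison is untouched. This is a low-cost improvement to an exploratory analysis and does not threaten the trial's main conclusion.

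**What to change.** **Sections 4.3 and 4.4.** Describe the control-group symptom items as uncontrolled change during the open Spark period. Report estimates with confidence intervals, and state that they do not support an effect of Spark.

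**Section 3.1.** Require the existing in-app PHQ-8 once, when controls first open Spark, and name that score as the starting value for the Spark-period PHQ-8 analysis. Add the time point to the schedule in section 3.4.

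**GAD-7, PROMIS and MFQ.** Where the post-control set is missing, do not use the enrolment baseline as the Spark-start value. Treat the start value as missing under the likelihood-based methods already planned, and keep these controls in the analysis.

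**Cost.** Some rewording, one additional showing of an 8-item questionnaire, and a weaker claim from this period.
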